6.4 Analysis of the Exploratory Efficacy Endpoints

Continuous and ordinal variables will be analyzed in a fashion similar to that of the primary endpoints, using the mixed model for crossover design on the ITT dataset.

6.4.1 Exploratory Endpoints

The exploratory endpoints in this study will be analyzed using the same mixed model as for the primary endpoints. The exploratory endpoints in this study are:

- Change from baseline in step time variability and step length variability measured on an electronic walkway system at the end of each treatment period
- Change from baseline in the mini-BESTest total score and subscores at the end of each treatment period
- Change from baseline in quantitative gait and balance measurements calculated by Opal APDM sensors during performance of the mini-BESTest battery at the end of each treatment period
- Change from baseline in the FOG score and freezing ratio, incorporating input from Opal APDM sensors during turning conditions, at the end of each treatment period
- Change from baseline in the FOG assessment by the rater on 0 to 4 ordinal scale can range from -4 to 4 and will also be analyzed using the same mixed model as for the primary endpoints
- Change from baseline in MDS-UPDRS Parts II and III subscores, PIGD and MDS-UPDRS 7-Item subscores at the end of each treatment period
- Change from baseline in UPSIT score at the end of each treatment period

6.4.2 Responder Analyses

The percentage of subjects with a 1-point, 3-point, and 5-point reduction in the MDS-UPDRS will be presented graphically overall by treatment, and then by subgroups of dementia type, baseline MMSE, and sex. No inferential statistics will be calculated to compare differences in proportion of subjects meeting each of these 3 thresholds after 2-week double-blind treatment period between treatment groups.

6.4.3 Other Analyses

If deemed appropriate, additional sensitivity analyses of the data not specified in the SAP may be undertaken and will be described in the clinical study report.

7 SAFETY SUMMARIES AND ANALYSES

The safety analysis will be descriptive in nature, and will be presented for the Safety Population. All safety data collected and captured in the CRF will be included in data listings sorted by domain, sequence, subject, and time point, or as appropriate. Mean changes from pre-treatment to on-treatment (Periods II and IV together) will be tabulated by treatment, while the number of subjects with potentially clinically significant values at pre-treatment and at the end of each double-blind two-week treatment period (Period II and Period IV) will be presented.

Generally, safety data will be presented for the Placebo Run-In Period, for the Double-Blind Treatment Period by treatment group (Period II and Period IV plus 7 days after the end of these periods, for the Washout Period starting at day 8 of the Washout Period, and for the post-treatment Follow-up Period starting at day 8 of the Follow-up Period.

All safety data will be summarized overall and then by stratified subgroup: dementia type (AD, LBD) and baseline MMSE (14-19 and 20-26).

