### **10.3. Data Analysis Considerations**

#### **10.3.1. Analysis Populations**

The primary population for safety analyses will be the Safety Population, which will consist of all subjects who were randomized and took at least one dose of investigational product.

The efficacy analysis population will consist of all randomized subjects who have taken at least one dose of investigational product and who have at least one post-baseline efficacy assessment. This will be the primary population used for the efficacy analysis.

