#### **10.4.1.1. Adverse Events**

AE verbatim text will be coded and classified by body system and preferred (coded) term using the Medical Dictionary for Regulatory Activities (MedDRA). AEs will be assigned to the treatment based on the last dose received. All AEs will be listed. AEs, Drug related AEs, SAEs, AEs that lead to discontinuation of investigational product will be summarized by treatment group. AEs will be summarized separately for the Single-Blind Run-In Period, the Double-Blind cross-over Treatment Period and the Follow-up Period.

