3.1.2 Run-In Population

All subjects entering the Placebo Run-in will be included in the Run-In population. This population will be used to provide an accounting of the disposition of subjects during this phase of the study.

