3.1.4 Safety Population

The Safety Population will consist of all subjects who were randomized and took at least one dose of double-blind investigational product.

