7.1 Adverse Events

Adverse events will be classified using the MedDRA version 18.1 coding dictionary. Tabulations will include an overall incidence of at least one adverse event, incidence within system organ class (SOC), and incidence by preferred term. Each subject may only contribute once per treatment group, that is by first occurrence to each of the incidence rates, regardless of the number of occurrences, as follows:

- Adverse events occurring prior to the first dose of double-blind investigational product will be referred to as Treatment-Emergent AEs (TEAEs) and presented as Placebo Run-In events.
- Adverse events occurring on or after the first dose of each double-blind two-week treatment period (Period II and period IV), and within 7 days of the last dose of double-blind investigational product, will be referred to as TEAEs and presented by treatment group.
- Events occurring 7 days after the last dose of Period II and Period IV and for the post-treatment Follow-up Period starting at day 8 (up to 14 days post-last-dose) will be presented as Post-Treatment Period. These events will only be included in a data listing.

Tabulations of the incidence of AEs will be presented as follows:

- Overview of TEAE
- TEAE by SOC and preferred term
- TEAE by preferred term
- TEAE by SOC, preferred term, and relationship to study drug
- TEAE by SOC, preferred term, and maximum severity (mild, moderate, and severe)

All AEs will be listed with its relationship to study drug and severity, flagging those which are not events during treatment-emergent period.

A listing of all deaths and serious AEs will be provided. Any TEAE leading to study drug temporary and permanent discontinuation will also be listed.

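### Placebo run-in AE incidence tables are planned on the Safety Population, so they omit events in subjects who left before randomization

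*SAP*

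**What the plan says.** The protocol (10.4.1.1) promises a run-in summary: "AEs will be summarized separately for the Single-Blind Run-In Period", alongside the double-blind and follow-up periods. SAP 7.1 carries this forward. Events before the first double-blind dose are to be "presented as Placebo Run-In events", and five incidence tabulations follow: an overview, by SOC and preferred term, by preferred term alone, by relationship and by maximum severity.

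The population is set at the start of SAP 7: "The safety analysis will be descriptive in nature, and will be presented for the Safety Population". The same section names the Placebo Run-In Period among the periods presented. SAP 3.1.4 defines the Safety Population as "all subjects who were randomized and took at least one dose of double-blind investigational product". Protocol 10.3.1 omits the word double-blind but also requires randomization: "which will consist of all subjects who were randomized and took at least one dose of investigational product".

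The SAP does define a population that fits the run-in. Section 3.1.2 says: "All subjects entering the Placebo Run-in will be included in the Run-In population". The only use it states is disposition: "This population will be used to provide an accounting of the disposition of subjects during this phase of the study". No visible section assigns run-in AE tables to it.

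**The concern.** A table meant to describe the run-in ought to cover everyone who took run-in medication. Here membership depends on what happened at the end of that period, so the group is selected after the fact. Protocol 6.6.1 counts a subject who leaves after entering the run-in as a study withdrawal, and such a subject has been dosed with placebo supplied as investigational product.

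What is at stake is the description of background AEs in a frail, fall-prone population. The run-in is the one all-placebo phase that precedes any possible exposure to intepirdine, so its AE incidence is a natural reference. There is also a reporting awkwardness. SAP 5.1 tabulates reasons for not completing the run-in on all entrants, so the report could show exits for AEs in the disposition table with no matching event in the run-in AE table.

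**Working it through.** The plan states no figure on this point, so there is nothing to reproduce. The check is a matter of who belongs to which set, followed by an illustration of size.

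**Membership**

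1. Run-in entry is at Visit 2, with the first placebo tablet taken in clinic (Protocol 7.1 and 8.1). All entrants form the Run-In Population (SAP 3.1.2).
2. Randomization is at Visit 3, after the run-in, and only for subjects who still meet all criteria, including gait speed (Protocol 7.2 and 8.1).
3. The Safety Population requires randomization and a double-blind dose (SAP 3.1.4).
4. A subject who leaves before randomization meets step 1 but not step 3. Such subjects therefore contribute nothing to any Safety Population table, whatever their reason for leaving.
5. Run-in AEs of subjects later randomized and dosed are still counted.

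The protocol's looser dose wording does not change step 4, because it also requires randomization. SAP 4.2 gives the SAP precedence in any case.

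**Size**

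Let R be the number randomized and dosed (30 to 40 planned, SAP 1.3), and k the number who leave the run-in because of an AE. The documents do not give k; I assume 1, 2 or 4. With no other run-in losses, the share of run-in entrants missing from the tables is k/(R + k):

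| R | k = 1 | k = 2 | k = 4 |
|---|---|---|---|
| 30 | 1/31 = 3.2% | 2/32 = 6.25% | 4/34 = 11.8% |
| 40 | 1/41 = 2.4% | 2/42 = 4.8% | 4/44 = 9.1% |

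To see the effect on the incidence of any run-in AE, assume also that a = 3 of those later randomized had a run-in AE. The planned table shows a/R; the Run-In Population would show (a + k)/(R + k):

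- R = 30: 3/30 = 10.0% as planned, against 4/31 = 12.9%, 5/32 = 15.6% or 7/34 = 20.6%.
- R = 40: 3/40 = 7.5% as planned, against 4/41 = 9.8%, 5/42 = 11.9% or 7/44 = 15.9%.

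**Direction**

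If a further m subjects leave without any AE, for example on the gait check, the full incidence is (a + k)/(R + k + m). This exceeds a/R only when k/(k + m) exceeds a/R, that is, when AEs are more frequent among leavers than among those who stay. The count of subjects with a run-in AE can only be too low. The percentage will usually be too low if AEs drive exits, but this is not guaranteed.

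**The case against.** The strongest reply is that little is hidden. SAP 7 lists all safety data captured on the CRF. SAP 7.1 lists every AE with relationship and severity, all deaths and serious AEs, and TEAEs leading to discontinuation, a label it also gives to run-in events. SAP 5.1 tabulates reasons for leaving the run-in on all entrants. All of that stands. What is missing is the leavers' share of the incidence tables.

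A second reply is that the SAP's choice keeps run-in and double-blind tables on the same people, a defensible like-for-like basis. That also stands, as a small cost of changing. A third is that table specifications sit in a separate spreadsheet (SAP 1), which may already name the right population, and that SAP 3.1.2 does not say disposition is the sole use of the Run-In Population. This is fair, but the SAP text as it reads points to the Safety Population and should be made to agree.

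Several stronger readings are tempting, and the documents do not support them:

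- A reader might infer that the run-in AE table will be empty. It will not; events in subjects later randomized and dosed are tabulated.
- A reader might infer that a rate of AEs leading to run-in exit will be reported as zero. SAP 7.1 plans no such tabulation; it lists those events.
- A reader might infer that the more severe events are the ones lost. That is plausible but not shown, and subjects can also leave for reasons unrelated to AEs.
- A reader might take the run-in as the only all-placebo phase. The washout (Period III) is also all placebo, and each completer takes double-blind placebo in Period II or IV.

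**Conclusion.** The point holds as a limited defect. Read as written, the run-in AE tables exclude anyone who left before randomization, from numerator and denominator alike, and so report incidence conditional on completing the run-in. The size is unknown. The range of about 2% to 12% of entrants rests on an assumed 1 to 4 AE leavers, 30 to 40 randomized and no other run-in losses.

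The comparison of intepirdine with placebo is untouched, because the excluded subjects took only single-blind placebo and were never randomized. This is a desirable correction to a descriptive table; no trial conclusion depends on it. The conclusion would fall away if the table specifications already use the Run-In Population, in which case the SAP text should simply say so.

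**What to change.** In SAP 7 and 7.1, state that Placebo Run-In AE and SAE summaries use the Run-In Population of SAP 3.1.2, with all run-in entrants as the denominator, and that double-blind summaries stay on the Safety Population. Extend the stated use of the Run-In Population in 3.1.2 to match, and check the table specifications against it.

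The cost is a sentence or two and a changed population flag on the run-in tables. No new data are needed, since AEs are collected from consent (Protocol 8.3.2.1.3). The one downside is that run-in and double-blind tables will have different denominators; a footnote on each run-in table can say so.

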7.1 Adverse Events

Adverse events will be classified using the MedDRA version 18.1 coding dictionary. Tabulations will include an overall incidence of at least one adverse event, incidence within system organ class (SOC), and incidence by preferred term. Each subject may only contribute once per treatment group, that is by first occurrence to each of the incidence rates, regardless of the number of occurrences, as follows:

- Adverse events occurring prior to the first dose of double-blind investigational product will be referred to as Treatment-Emergent AEs (TEAEs) and presented as Placebo Run-In events.
- Adverse events occurring on or after the first dose of each double-blind two-week treatment period (Period II and period IV), and within 7 days of the last dose of double-blind investigational product, will be referred to as TEAEs and presented by treatment group.
- Events occurring 7 days after the last dose of Period II and Period IV and for the post-treatment Follow-up Period starting at day 8 (up to 14 days post-last-dose) will be presented as Post-Treatment Period. These events will only be included in a data listing.

Tabulations of the incidence of AEs will be presented as follows:

- Overview of TEAE
- TEAE by SOC and preferred term
- TEAE by preferred term
- TEAE by SOC, preferred term, and relationship to study drug
- TEAE by SOC, preferred term, and maximum severity (mild, moderate, and severe)

All AEs will be listed with its relationship to study drug and severity, flagging those which are not events during treatment-emergent period.

A listing of all deaths and serious AEs will be provided. Any TEAE leading to study drug temporary and permanent discontinuation will also be listed.

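### SAP 7.1's first-occurrence rule, applied as written to the AE table by relationship, can miss a later and more strongly related event; in the severity table it clashes in wording with the maximum-severity label

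*SAP*

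**What the plan says.** SAP 7.1 first names three rates: "Tabulations will include an overall incidence of at least one adverse event, incidence within system organ class (SOC), and incidence by preferred term". The counting rule follows directly: "Each subject may only contribute once per treatment group, that is by first occurrence to each of the incidence rates".

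The section then lists five tabulations of AE incidence. In two of them an attribute of the event decides the cell:

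- "TEAE by SOC, preferred term, and relationship to study drug"
- "TEAE by SOC, preferred term, and maximum severity (mild, moderate, and severe")

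The second carries its own selection rule in its title. The first carries none, and SAP 7.1 does not say how to place a subject whose events were given different relationships.

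SAP 7.1 also plans listings: "All AEs will be listed with its relationship to study drug and severity, flagging those which are not events during treatment-emergent period", and "A listing of all deaths and serious AEs will be provided".

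Protocol 10.4.1.1 requires that "AEs, Drug related AEs, SAEs, AEs that lead to discontinuation of investigational product will be summarized by treatment group". Protocol 8.3.2.1.4 grades causality on five levels: certain, probable, possible, unlikely, not related. SAP 4.2 gives the SAP precedence where the two documents differ.

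**The concern.** First occurrence decides which event represents the subject. That choice does not matter when the question is only whether any event occurred. It matters once the representing event's relationship or severity determines the cell.

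Read literally, the rule would put a subject with an unlikely event followed by a probable one in the unlikely category. Safety and tolerability is the trial's only secondary objective, and the relationship table is the one tabulation in SAP 7.1 explicitly described as showing drug relationship by treatment. Two programmers working from this text could produce different tables, so the choice should be fixed before unblinding.

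Elsewhere the SAP states a worst-case rule where it wants one: the most extreme value in the laboratory tables (7.2), the highest QTcF (7.4), and the maximum in the severity table. The relationship table has no such statement.

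**Working it through.** The documents state no AE rate, repeat-event rate or share of related events, so there is no planned figure to reproduce. The check is of the text, followed by an illustration on assumed inputs.

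**Step 1: what the rule does to one subject.** Take an invented subject with two events under one treatment: dizziness on day 3 (mild, unlikely) and dizziness on day 10 (severe, probable).

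| Tabulation | By first occurrence | By worst or strongest event |
|---|---|---|
| Any event: overall, SOC, preferred term | counted once | counted once |
| Relationship | unlikely | probable |
| Severity | mild | severe |

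The first row is the same either way, so the plain incidence tables lose nobody. In the third row the table's title already asks for the maximum, so there the two instructions in SAP 7.1 disagree. In the second row nothing in SAP 7.1 overrides first occurrence.

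**Step 2: direction.** Fix a table row and a treatment. Subjects whose first event is related are a subset of subjects with at least one related event. Classifying by first event therefore gives a related count that is equal or lower, never higher.

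**Step 3: who can be affected.** Only subjects with two or more events in the same row under the same treatment. In a preferred-term row the same term must recur. In a SOC or overall row, different terms suffice. SAP 7.1 counts treatment-emergent events up to 7 days after the last double-blind dose, so each window is about two weeks plus 7 days.

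**Step 4: illustrative size.** Assume a subject has k events in a row, each independently judged related with probability q.

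- Counted as related by first event: q
- Has at least one related event: 1 − (1 − q)^k
- Relative undercount: 1 − q / [1 − (1 − q)^k]

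| k | q | First event | Any related event | Relative undercount |
|---|---|---|---|---|
| 1 | any | q | q | 0% |
| 2 | 0.10 | 0.10 | 0.19 | 47% |
| 2 | 0.30 | 0.30 | 0.51 | 41% |
| 2 | 0.50 | 0.50 | 0.75 | 33% |
| 3 | 0.30 | 0.30 | 0.657 | 54% |

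These rows describe only subjects with k events. Across all subjects with an AE, let a fraction f have two events and the rest one, with q = 0.30. The correct proportion is (1 − f) × 0.30 + f × 0.51.

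- f = 0.10: 0.321; undercount 1 − 0.30/0.321 = 6.5%
- f = 0.25: 0.3525; undercount 1 − 0.30/0.3525 = 15%
- f = 0.50: 0.405; undercount 1 − 0.30/0.405 = 26%

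If 20 subjects had an AE, the rule would show 20 × 0.30 = 6.0 as related, where the correct expected numbers are about 6.4, 7.0 and 8.1.

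**Step 5: weight of one subject.** With 30 to 40 subjects, each receiving both treatments if they complete, one reclassified subject moves a percentage by 1/40 = 2.5 to 1/30 = 3.3 points.

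**The case against.** The strongest reply is that the rule was never meant for the classified tables. The sentence before it names only the overall, SOC and preferred-term rates, and *each of the incidence rates* can be read as referring to those three. This is plausible. But the relationship table would then have no rule at all, which still needs repair, and the SAP itself introduces all five tables as tabulations of incidence.

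A second reply is that first occurrence can be taken within each relationship category, which keeps the later related event. That reading would place one subject in two categories of the same row, which is hard to reconcile with contributing only once per treatment group. Similarly, the protocol's drug-related summary could be built by selecting related events first and then counting subjects. That would be correct, but SAP 7.1 names no such table. It does not describe the contents of its overview table, which might include such a row.

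Third, SAP 1 places table specifications in a separate spreadsheet, so a convention may exist there. The SAP text should still state it.

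A reader might also infer more than the documents support:

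- *That every AE table is affected.* It is not; Step 1 shows the plain incidences are unchanged.
- *That later severe events go uncounted.* The maximum-severity title is specific to its own table and most naturally governs it. What remains is a conflict in wording.
- *That drug-related events will in fact be understated, and most in the treatment with more events.* The first depends on the literal reading. The second also needs similar relatedness and event order under both treatments, which nothing in the documents establishes.
- *That events vanish from the report.* All AEs are listed with relationship and severity, and deaths and SAEs are listed separately. Listings do not, however, give percentages by treatment.

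The illustration is also generous to the concern. Independence is assumed, and if causality judgements within a subject are positively correlated, the gap shrinks.

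**Conclusion.** The point holds for the relationship table. As written, the only counting rule in SAP 7.1 classifies a subject by the first event, and any resulting error goes one way, towards fewer drug-related events. For the severity table the point is limited to inconsistent wording.

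The size is unknown. The 15% to 26% range follows from assuming q = 0.30, independence, and two events in 25% to 50% of subjects with an AE; none of these comes from the documents. Safety is analysed descriptively, so no test or decision rule is affected. This is a modest correction to a stated rule, worth making because the table is small, each subject carries 2.5 to 3.3 percentage points, and the choice should not be left to programming after unblinding.

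**What to change.** In SAP 7.1, confine first occurrence to the at-least-one-event rates and add a rule for the classified tables, for example:

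*For rates of at least one event, each subject is counted once per treatment, by first occurrence. In the tables by severity and by relationship, each subject is counted once per treatment at each level (overall, SOC, preferred term): at the highest severity in the severity table and at the strongest relationship in the relationship table, among that subject's treatment-emergent events at that level under that treatment.*

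The order of the relationship categories should be stated as the five levels in protocol 8.3.2.1.4, and the separate table specifications checked for agreement.

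The cost is a short text change and no new data. The downside for the sponsor is that related-event percentages may become slightly less favourable.
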